## **7.5 Concomitant Therapy**

### **7.5.1 Phosphate Lowering Therapy**

Investigators may continue or newly prescribe non-Auryxia phosphate lowering therapy as needed throughout the study to maintain serum phosphorus according to the local community standard.

Commercial Auryxia may not be prescribed to any subject for the duration of the study. See Section 7.5.4

In the event of an adverse event of special interest (serum phosphorus  $<2.5$  mg/dL), the Investigator must review other prescribed phosphate-lowering therapies and make adjustments accordingly. Additionally, in the event of a serum phosphorus  $<3.0$  mg/dL, other prescribed phosphate lowering therapy may also require adjustment as per Section 7.1.2.1.

All changes in phosphate-lowering therapy will be captured in source documentation and in the eCRF.

### **7.5.2 Iron Supplementation**

Investigators may continue or newly prescribe iron supplementation (IV, oral) as needed throughout the study to maintain ferritin and TSAT according to the local community standard with the exception of protocol required safety changes in study drug as outlined in Section 7.1.2.1.

In the event of an adverse event of special interest (iron overload), the Investigator must review other prescribed iron supplementation (IV and oral) and make adjustments accordingly. Additionally, in the event of elevated iron indices (TSAT  $>45\%$  or ferritin  $>500$  ng/mL), other prescribed oral or IV iron therapy may also require adjustment as per Section 7.1.2.1.

All changes in iron supplementation therapy will be captured in source documentation and in the eCRF.

### **7.5.3 Erythropoiesis-Stimulating Agents (ESAs) or Packed Red Blood Cell (PRBC) Transfusion**

There are no restrictions on the use of ESA and dose adjustments may be made at the discretion of the Investigator. All changes in ESA therapy will be captured in source documentation and in the eCRF

Receipt of RBC transfusions will be captured in source documentation and in the eCRF.

- Subjects who receive repeated red blood cell transfusions during the study may need to temporarily hold study drug. For the purpose of the study, “repeated blood transfusion” will be defined as receipt of >4 units of red blood cells within any 6-month period of time. Prior to study drug hold please contact the medical monitor. If study drug is permanently discontinued, subsequent study visits including the Follow Up visit (Visit 6) should occur per the SoA.

### **7.5.4 Prohibited Medications/Procedures**

Potentially eligible subjects may or may not be receiving phosphate-lowering or iron-repletion therapy prior to Day 1; however, if a subject is receiving commercial ferric citrate (Auryxia), it must be stopped at or prior to Day 1.

Prescription of commercial Auryxia is prohibited for all subjects at any time after Day 1/Baseline in the study. All other therapies may be administered per SOC. Receipt of commercial Auryxia for longer than 4 consecutive weeks during trial participation will be considered a protocol deviation. If the Investigator is unwilling to discontinue commercial Auryxia, study drug should be discontinued, and the subject should continue to be followed per the SoA including the Follow Up Visit (Visit 6).

Since ferric citrate will be administered to 50% of subjects, standard drug-drug interactions reported in the Auryxia package insert approved by the Food and Drug Administration (FDA) in the US shall be followed. [Auryxia USPI 2021].

### **7.5.5 Permitted therapy**

There are no restrictions on use of any concomitant medications other than that identified in Section 7.5.4

### **7.5.6 Potential Drug-Drug Interactions**

An interaction with ferric citrate is known to occur with doxycycline and ciprofloxacin. If prescribed, doxycycline should be taken at least 1 hour before study drug and ciprofloxacin should be taken at least 2 hours before or after study drug.

The following drugs, by drug category, did **not** show an interaction with ferric citrate:

- Antibiotics: levofloxacin.
- Anticoagulants/antiplatelets: aspirin, clopidogrel, and warfarin.
- Antidiabetics: glimepiride and sitagliptin.

- Antihyperlipidemics: atorvastatin, fluvastatin, and pravastatin.
- Antihypertensives: amlodipine, diltiazem, enalapril, losartan, metoprolol, and propranolol.
- Cardiac glycoside: digoxin.
- Vitamin D analogs: calcitriol and doxercalciferol.

Consider separation of the timing of the administration of study drug with drugs where a reduction in their bioavailability would have a clinically significant effect on safety or efficacy. The duration of separation depends upon the absorption characteristics of the medication concomitantly administered, such as the time to reach peak systemic levels and whether the drug is an immediate release or an extended-release product. Consider monitoring clinical responses or blood levels of concomitant medications that have a narrow therapeutic range.

## **8.0 DISCONTINUATION OF STUDY INTERVENTION AND PARTICIPANT DISCONTINUATION/WITHDRAWAL**

### **8.1 Discontinuation of Study Drug**

#### **8.1.1 Temporary Interruption of Study Drug**

Discontinuation from study drug is different from discontinuation from the study, and remaining study procedures will be completed as indicated by the study protocol. The Investigator is strongly encouraged to resume study drug as soon as the reason for temporary interruption is over. Reasons for temporary discontinuation of study drug include:

- Drug-related AEs per the Investigator's discretion
- Unforeseen circumstances per the Investigator's discretion
- Serum phosphorus <3.0 mg/dL
- TSAT is >50%
- Ferritin >500 ng/mL
- Repeated red blood cell transfusions (>4 units of red blood cells within any 6-month period of time). See Section 7.5.3.
- Significant elevation in liver enzymes (SGOT and/or SGPT) >3X ULN or pancreatic enzymes (amylase and/or lipase) >2X ULN or elevation in total bilirubin >2X ULN, without an identifiable alternate etiology. Study drug should not be resumed prior to discussion with Medical Monitor.

The study drug may be restarted when the reason for temporary discontinuation is resolved. If study drug is temporarily discontinued due to elevations in iron indices, both TSAT and ferritin laboratory values must be within protocol-defined ranges prior to resumption of study drug.

The data to be collected at the time of study drug discontinuation should be in accordance with the SoA.

### **8.1.2 Permanent Discontinuation of Study Drug**

Subjects are free to withdraw from taking study drug at any time upon request. Subjects who permanently discontinue study drug will be asked to continue study participation (either by in person visits or by allowing access to medical records) in accordance with the SoA, through completion of the study. The endpoint assessment will be considered the End of Study date.

If a subject declines to continue study visits and withdraws consent to be followed, the subject is an early termination, and NO endpoint assessment will be performed. The subject's early termination date will be considered the End of Study date.

An Investigator **may** discontinue study drug or withdraw a subject from the study for the following reasons:

- Pregnancy
- Significant study intervention non-compliance
- If any clinically significant AE, laboratory abnormality, or other medical condition or situation occurs such that continued participation in the study would not be in the best interest of the subject
- Iron overload supported by liver biopsy, magnetic resonance imaging and persistent elevations in TSAT or ferritin
- If the TSAT remains >50%; Refer to Section 7.1.2.1
- If the ferritin remains >500 ng/mL; Refer to Section 7.1.2.1
- If the serum phosphorus remains <3.0 mg/dL; Refer to Section 7.1.2.1
- Investigator-Sponsor decision
- Lost to follow-up

The reason for study drug discontinuation will be recorded in source documentation and in the eCRF.

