If after a 50% reduction in total daily dose of study drug, the TSAT is  $>50\%$ , the study drug should be temporarily held. Subsequent study visits including the Follow Up visit (Visit 6) should continue to be conducted as per the SoA (regardless of study drug administration). When TSAT is  $\leq 50\%$ , study drug may be resumed. Other prescribed oral or IV iron therapy may be resumed per investigator discretion when TSAT is  $\leq 45\%$ .

Required dose adjustments for high ferritin are as follows:

- If serum ferritin is  $>500$  ng/mL, captured by a single laboratory value, the study drug, and any other prescribed oral or IV iron therapy, should be temporarily held until such time as ferritin is  $\leq 500$  ng/mL (captured by a single laboratory value) at which time study drug may be resumed at a dose that is equivalent to 50% of the current total daily dose. The reduction in dose relative to meals or snacks is at the discretion of the investigator as long as it represents a total dose reduction of 50%. Repeat assessment of iron indices will be at the discretion of the Investigator. This assessment must occur at the next scheduled visit (which may be up to three months), or it may also be performed earlier.

- If after a 50% reduction in total daily dose of study drug, the serum ferritin is  $>500$  ng/mL, the study drug should be temporarily held. Subsequent study visits including the Follow Up visit (Visit 6) should continue to occur per the SoA (regardless of study drug administration). When serum ferritin is  $\leq 500$  ng/mL, study drug may be resumed. Other prescribed oral or IV iron therapy may be resumed per investigator discretion when ferritin is  $\leq 500$  ng/mL.

Both TSAT and ferritin laboratory values must be within ranges defined above prior to resumption of study drug.

Study drug may be titrated downward at any time during the treatment period at the discretion of the Investigator for adverse reactions determined to be related to study drug.

**There is no minimum allowable dose of study drug, and the Investigator has discretion to resume dosing up to 6 tablets/day based on subject acceptance when possible (and when TSAT, ferritin, and phosphorus values are within protocol-defined ranges).**

All dose adjustments should be captured in the subject specific source documentation and the eCRF.

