## **7.4 Study Intervention Compliance**

Study personnel will instruct the subjects and caregivers on the correct number of tablets to take each day with their meals or snacks. Subjects will be instructed to return with their bottle(s) of study drug at each in-person visit so that compliance may be assessed. Unused study drug will be re-dispensed to the subject at the end of each in-person visit.

Throughout the study, subjects will be questioned regarding dosing compliance and whether they have questions or have experienced any problems related to the dosing of study drug. The Investigator or designee will also maintain study drug accountability itemizing all study drug dispensed to and returned from each subject during the study. Treatment compliance will be determined from these logs and subject questioning.

Subjects who miss doses will be counseled on the importance of compliance. Subjects will not be withdrawn from the study for reasons related to study drug compliance.

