## **10.3 Missing Data**

Discontinuation from study intervention is different from discontinuation from the study, and remaining study procedures will be completed as indicated by the study protocol unless the subject withdraws consent for participation in the study.

All data pertaining to the primary and secondary endpoints collected at any point during the study, both during study drug treatment and post-study drug treatment discontinuation, will be used for the primary analysis of the endpoints and its individual components.

Unless stated otherwise in the Statistical Analysis Plan, missing data for all other endpoints will not be imputed and the analysis will be based on observed data.

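### Protocol 8.1.2 uses one reason list for stopping drug and for leaving the study; its non-compliance reason conflicts with 7.4, and endpoint follow-up after an Investigator-initiated withdrawal is not stated

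*Protocol*

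**What the plan says.** Protocol 8.1.2 concerns permanent discontinuation of study drug. Its first paragraph says that subjects who stop drug "will be asked to continue study participation (either by in person visits or by allowing access to medical records"), through completion of the study. Its second says that a subject who withdraws consent to be followed has no endpoint assessment. It then says that an Investigator may "discontinue study drug or withdraw a subject from the study for the following reasons". The nine reasons include "Significant study intervention non-compliance", clinically significant adverse events or laboratory abnormalities, persistently high TSAT or ferritin, persistently low phosphorus, and an Investigator-Sponsor decision. Nothing says which reasons lead to which action.

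Other passages bear on this:

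- **Protocol 7.4:** "Subjects will not be withdrawn from the study for reasons related to study drug compliance".
- **Protocol 7.1.2.1**, to which the TSAT, ferritin and phosphorus reasons refer, says for ferritin (and similarly for TSAT): "Subsequent study visits including the Follow Up visit (Visit 6) should continue to occur per the SoA (regardless of study drug administration").
- **Protocol 8.1.1:** "Discontinuation from study drug is different from discontinuation from the study, and remaining study procedures will be completed as indicated by the study protocol".
- **Protocol 10.3**, on stopping study intervention: "remaining study procedures will be completed as indicated by the study protocol unless the subject withdraws consent for participation in the study". It then brings endpoint data collected after drug discontinuation into the primary analysis.
- **Protocol 8.2** names consent withdrawal, maintenance dialysis and kidney transplant as reasons for leaving the study. Withdrawal by the Investigator is not among them.
- **SAP 3.5** counts adverse event and investigator decision among the reasons for ending the study.

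**The concern.** There are two problems. First, 8.1.2 permits, on its withdrawal limb, something that 7.4 rules out. That 8.1.2 only says the Investigator may do it does not remove the conflict. More generally, allowing withdrawal from the study under this list fits poorly with 7.1.2.1, 8.1.1, 8.2 and 10.3, all of which separate drug from participation.

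Second, if an Investigator uses the withdrawal limb, no text says what happens to endpoint ascertainment. Several listed reasons can depend on treatment: ferric citrate lowers serum phosphorus (Protocol 3.3.2), and iron accumulation is a potential risk (3.3.1). Ending outcome follow-up for such reasons could censor the primary endpoint informatively. If withdrawal differs by arm and the withdrawn subjects differ in risk, the Cox hazard ratio shifts.

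**Working it through.** **1. Is endpoint follow-up stated for each route?**

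| Route | What the documents state |
|---|---|
| Drug stopped, subject stays in study | Continue per the Schedule of Activities (8.1.2, first paragraph; also 7.1.2.1, 7.5.3, 7.5.4) |
| Unblinded | Called an early termination, but followed under 8.1.2 (7.3.2) |
| Consent to be followed withdrawn | No endpoint assessment (8.1.2) |
| Dialysis or transplant | 30-day vital status check (8.2) |
| Lost to follow-up | Dialysis, transplant and vital status sought from available sources (8.3) |
| Withdrawn by Investigator or Investigator-Sponsor, consent not withdrawn | Not stated |

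Two passages come near the last row. Schedule of Activities footnote D sets a visit 30 days after last dose for SAEs and vital status, without naming dialysis. The endpoint assessments at Months 3, 6, 9 and 10 do include dialysis (footnote O). Neither is said to apply after such a withdrawal.

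**2. The SAP cap.** SAP 3.3 caps the vital status date 37 days after early termination. The protocol uses that term for undosed subjects (6.3), unblinded subjects (7.3.2) and consent withdrawal (8.1.2, 8.2); the SAP disposition shell uses its abbreviation more broadly. Whether it covers Investigator-withdrawn subjects is unclear. If it did, a Day 180 withdrawal would have vital status to Day 180 + 37 = 217, which is 300 − 217 = 83 days short of Month 10.

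**3. The plan's own event count, for scale.** With 0.94 events per person-year and 0.75 years, the control probability is 1 − exp(−0.94 × 0.75) = 0.506. At hazard ratio 0.60 the treated probability is 1 − exp(−0.94 × 0.60 × 0.75) = 0.345. With 200 per arm this gives about 170 events. Freedman's formula needs 169 events (398 subjects) for 90% power, which agrees with the planned 400. The standard error of the log hazard ratio is 2/√170.2 = 0.153.

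**4. Size of a shift under assumed rates.** The documents give none, so every rate here is an assumption. In each arm a share p = 0.15 is prone to withdrawal, with hazard k times that of the others. A fraction w of the prone subjects is withdrawn at time s, with no endpoint data afterwards. The others' control hazard is h = 0.94/(1 − p + pk), which keeps the mean at 0.94: 0.817 for k = 2 and 1.016 for k = 0.5. With θ = 1 on placebo and the true hazard ratio on ferric citrate, the expected at-risk share in an arm is

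R(t) = (1 − p)·exp(−hθt) + p·[1 − w·1(t > s)]·exp(−khθt),

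and the event density f(t) weights the two terms by hθ and khθ. The expected Cox estimate b solves

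∫ [f₁ − (f₁ + f₀)·R₁eᵇ/(R₁eᵇ + R₀)] dt = 0 over 0 to 0.75 years.

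For a true hazard ratio of 1.00, exp(b) is:

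| Withdrawal day | w, ferric citrate v placebo | k = 2 | k = 1 | k = 0.5 |
|---|---|---|---|---|
| 180 | 100% v 20% | 0.982 | 1.000 | 1.021 |
| 180 | 50% v 20% | 0.993 | 1.000 | 1.008 |
| 90 | 100% v 20% | 0.955 | 1.000 | 1.047 |

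Day 180 suits the laboratory reasons. A value that remains out of range needs a repeat, the first scheduled treatment-period laboratory results are at Month 3, and on reassessment 7.1.2.1 says "This assessment must occur at the next scheduled visit (which may be up to three months), or it may also be performed earlier". Non-compliance, adverse events and sponsor decisions need not wait that long, hence Day 90.

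On the log scale, the Day 90 shifts are about 0.046 in size, or 0.046/0.153 = 0.30 of the standard error above. At a true hazard ratio of 0.60 with Day 180 withdrawal, the estimate moves by at most 0.014 against complete follow-up. At most 5 events are lost, which alone costs at most 0.8 points of Schoenfeld power. If the shifted hazard ratio is also used, power moves between +1.7 points (k = 2) and −2.8 points (k = 0.5).

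**The case against.** The best defence is that the default text already covers nearly everything. Section 8.1.2 is about drug, and its closing line records only the reason for stopping drug. Study withdrawal has its own section. Sections 7.1.2.1, 7.3.2, 7.5.3, 7.5.4, 8.1.1 and 10.3 all keep follow-up going after drug is stopped or held, and 10.3 excepts only consent withdrawal. On that reading, the reference to withdrawing a subject is a stray phrase. Bias would need three things together: differential withdrawal, different risk in those withdrawn, and sites ending follow-up.

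Much of this stands, and it limits the size of the point. It does not close the gap. The rule in 10.3 is about stopping the intervention, the 8.2 list does not address this route, and SAP 3.5 expects exits by investigator decision. Protocol 11.10.2 also has the Investigator-Sponsor judge, after a deviation, whether the subject continues in the study.

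A reader might infer that the plan stops endpoint follow-up whenever drug is stopped, or that the primary analysis is materially biased. The documents support neither: most drug stops have explicit continued follow-up, and no withdrawal rate is given. Nor can one infer that stopping drug for non-compliance breaches 7.4, or that the 37-day cap certainly applies to these subjects.

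**Conclusion.** The point holds and is minor. The conflict between 8.1.2 and 7.4 is direct, though only for withdrawal from the study. The missing rule for subjects withdrawn by the Investigator or Investigator-Sponsor without consent withdrawal is real. Both follow from the text and need no assumed rate.

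The consequence for the hazard ratio is probably small, and its direction is unknown. The illustrations rest on an assumed prone share, assumed withdrawal fractions, an assumed relative hazard and no endpoint data after withdrawal. They are not bounds: moving withdrawal from Day 180 to Day 90 roughly doubles the shift. The case for acting is that the safeguard is cheap, not that a large bias has been shown.

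**What to change.** 1. Reconcile 8.1.2 with 7.4 and 7.1.2.1 by stating for each listed reason whether it applies to study drug, to study participation, or to both. No treatment-stopping reason need change, and this review takes no position on which passage is right.
2. Add to 8.1.2 and 8.2: *Except after maintenance dialysis or kidney transplant, where the 30-day vital status check applies, a subject who stops study drug or study visits for any reason, and has not withdrawn consent to be followed, has dialysis, transplant and vital status (and hospitalization where records allow) ascertained by visits or records through the Month 10 EOS visit (Day 300).*
3. Define early termination once. State in SAP 3.3 that the 37-day cap does not apply to subjects whose endpoint follow-up continues, including unblinded subjects followed under 8.1.2.
4. SAP 3.5 already tabulates reasons for ending the study by arm. Add a separate table, by arm, of reasons for stopping study drug.

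The cost is protocol and SAP wording, a note to sites and a few record checks. Record access is already foreseen in the first paragraph of 8.1.2, and record-based ascertainment of dialysis status in 8.3.

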## 6.2 Exclusion Criteria

1. Patients who, in the opinion of the Investigator, have acute kidney injury rather than CKD.
2. Patients with planned/imminent maintenance dialysis, or that are anticipated to begin maintenance dialysis within 8 weeks from Screening, in the opinion of the Investigator.
3. A known allergy or intolerance to ferric citrate or any of its constituents.
4. Hypersensitivity reaction to previous oral iron therapy.
5. History of hemochromatosis or iron overload syndrome (e.g., hereditary sideroblastic anemia, thalassemia, polycythemia vera).
6. Active malignancy requiring current treatment except for non-melanoma skin cancer regardless of treatment.
7. Active drug or alcohol dependence or abuse (excluding tobacco use or use of medical or recreational marijuana) within the 12 months prior to Screening or evidence of such abuse, in the opinion of the Investigator.
8. Limited life expectancy ( $<6$  months) in the opinion of the Investigator.
9. Females who are known to be pregnant or are breast-feeding during Screening or are planning to become pregnant and breastfeeding during the study period.
10. Evidence of a clinically active infection requiring antibiotics at Randomization.
11. Unable to comply with study requirements or in the opinion of the Investigator, not clinically stable to participate in the study.
12. Use of an investigational medication or participation in an investigational study within 30 days prior to Day 1.
13. Patients with a scheduled date for receipt of living donor kidney transplant.

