**As such, adverse events will only be collected in the following instances:**

If they meet the definition of an SAE (see Section 9.6.1.2) or meet the requirements for reporting as an IND safety report. If there is any doubt whether the information constitutes an AE or SAE, please contact the Medical Monitor for discussion.

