#### **Adverse Events of Special Interest:**

- If an event of iron overload occurs it will be captured as an adverse event of special interest. Iron overload is defined as any liver biopsy findings or MRI imaging consistent with this diagnosis in the setting of persistent TSAT >45%. In the event of an adverse event of special interest, the Investigator must review other prescribed iron supplementation (IV and oral) and make adjustments in accordance with Section 7.1.2.1.
- If a clinically significant episode of hypophosphatemia occurs it will be captured as adverse events of special interest. Clinically significant hypophosphatemia is defined as serum phosphorus <2.5 mg/dL. In the event of an adverse event of special interest, the Investigator must review other prescribed phosphate-lowering therapies and make adjustments in accordance with Section 7.1.2.1.

Subjects will be followed for protocol required SAEs and AEs of special interest until the final required protocol visit or until all drug-related toxicities and AEs have resolved (or are considered chronic/stable), whichever is later.

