#### **9.6.4    Reporting Adverse Events**

Non-serious AEs (with the exception of Adverse Events of Special Interest in Section 9.5.2) will not be collected in source documents or reported in the eCRF.

All SAEs will be collected in source documents and reported in the eCRF.

All Adverse Events of Special Interest will be collected in the source documents and reported in the eCRF.

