#### 3.6.1. Analysis of Adverse Events

Analyses of safety data will use the safety population and will only be conducted for SAEs, related SAEs, AESI, and laboratory values.

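### The iron-overload AESI requires raised TSAT and has no ferritin route, although the protocol's own stopping reason accepts either index, so some confirmed non-serious cases would not be counted

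*Protocol*

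**What the plan says.** Iron overload is described in two ways.

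- **As a stopping reason.** Protocol 8.1.2 gives the Investigator discretion to stop study drug or withdraw a subject for several reasons, one being "Iron overload supported by liver biopsy, magnetic resonance imaging and persistent elevations in TSAT or ferritin". Either index qualifies, and no numeric limit is attached.
- **As a counted event.** Protocol 9.5.2 states: "Iron overload is defined as any liver biopsy findings or MRI imaging consistent with this diagnosis in the setting of persistent TSAT >45" (per cent). SAP 3.6.1 repeats this definition. Ferritin does not appear in it.

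Three other parts of the plan decide what follows from the difference.

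- **Collection.** Protocol 9.5.2 gives the condition for collecting an adverse event as: "If they meet the definition of an SAE (see Section 9.6.1.2) or meet the requirements for reporting as an IND safety report". AESIs are then added. Protocol 9.6.4 says that non-serious events other than AESIs "will not be collected in source documents or reported in the eCRF".
- **Analysis.** SAP 3.6.1 states: "Analyses of safety data will use the safety population and will only be conducted for SAEs, related SAEs, AESI, and laboratory values".
- **Status of ferritin.** Protocol 7.5.2 treats TSAT above 45% or ferritin above 500 ng/mL as elevated iron indices. Section 8.1.1 lists "Ferritin >500 ng/mL" as a reason to interrupt study drug, separately from TSAT, and 8.1.2 lists ferritin that stays above that level as a possible reason to stop.

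**The concern.** Protocol 3.3.1 names iron accumulation, with possible organ damage, as a potential risk of long-term treatment, and iron overload is one of only two AESIs in the trial. A reader of the safety results will look to the AESI table for confirmed cases. Elsewhere the protocol treats ferritin as an iron-safety signal in its own right, yet the AESI definition leaves it out and gives no reason. Because routine non-serious events are not collected, a case outside the AESI definition has no ordinary adverse-event record to fall back on. What is at stake is the completeness of one safety count, not the efficacy conclusion.

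**Working it through.** No figure in the plan depends on this point, so there is nothing to recalculate. The check sets the two texts side by side and runs the possible cases through the collection rules.

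**Step 1: compare the wording.**

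| Element | Protocol 8.1.2 (may stop drug) | Protocol 9.5.2 and SAP 3.6.1 (AESI) |
|---|---|---|
| Tissue or imaging evidence | Biopsy and MRI, listed together with the index and joined by *and* | Biopsy *or* MRI |
| Iron index | TSAT *or* ferritin | TSAT only |
| Numeric limit | None given | Above 45% |

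**Step 2: classify a confirmed, non-serious case.** Here 8.1.2 is read as satisfied by biopsy or MRI, and ferritin is called raised above 500 ng/mL, the level in 7.5.2.

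| Case | TSAT persistently above 45% | Ferritin persistently raised | Fits 8.1.2 | Meets AESI definition | Collected as an AESI |
|---|---|---|---|---|---|
| A | Yes | Either | Yes | Yes | Yes |
| B | No | Yes | Yes | No | No |
| C | No | No | No | No | No |

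Case B is the gap. The protocol recognises it as iron overload when listing reasons to stop drug, but it cannot enter the AESI count.

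**Step 3: see whether the strict reading of 8.1.2 closes the gap.** Suppose 8.1.2 requires both biopsy and MRI. A subject with both findings, high ferritin and TSAT not persistently above 45% still fits 8.1.2 and still fails the AESI definition. The gap therefore does not depend on how that bullet is read.

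**Step 4: follow case B through collection and analysis.** The event is not serious and not an AESI. Unless it is reportable as an IND safety report, 9.5.2 and 9.6.4 keep it out of the adverse-event data. SAP 3.6.1 restricts the safety analysis to SAEs, related SAEs, AESIs and laboratory values, so the case adds nothing to the AESI row in the SAP's table shell for all adverse events.

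**Step 5: look for other records of the case.**

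- The reason for stopping drug is recorded in the eCRF, if drug is stopped (8.1.2).
- Dose adjustments are recorded in the eCRF (7.1.2.1).
- The Investigator must review and document the clinical significance of each iron result (9.4).
- Ferritin and TSAT are summarised at each visit (SAP 3.6).
- Medically important events count as serious, and doubt about seriousness is resolved in favour of an SAE (9.6.1.2).

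These records may leave traces of the case, but none of them adds it to the AESI count.

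**The case against.** The best answer is that the plan contains only one definition. Protocol 9.5.2 and SAP 3.6.1 agree exactly on what is counted, while 8.1.2 is a discretionary list, and a permissive stopping reason may reasonably be wider than a counted event. The case at issue is also narrow: a biopsy or MRI that the plan does not schedule, high ferritin without persistently high TSAT, a judgement that the event is not serious, and at most nine months of treatment. Step 5 shows that such a case need not vanish. All of this stands, and it limits the point to a minor one. It does not explain why ferritin, which triggers a hold by itself, is left out of the count.

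A reader might go further in several directions that the documents do not support.

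- *That the AESI row is the only place such a case could appear.* The records in step 5 contradict this.
- *That 9.5.2 points to a section with no relevant rule.* It sends the reader to 7.1.2.1 for adjusting other iron, and 7.1.2.1 has rules for that, as well as for study drug, keyed to TSAT and ferritin.
- *That 8.1.1 is deficient because it does not name iron overload.* It lists both raised indices and drug-related adverse events as reasons for interruption.
- *That exclusion criterion 5 conflicts with 8.1.2.* That criterion, "History of hemochromatosis or iron overload syndrome", gives pre-existing disorders as its examples and says nothing about accumulation during the study.
- *That the TSAT condition can hardly be met because dose is cut once TSAT passes 45%.* Sections 7.1.2.1 and 8.1.2 both foresee TSAT staying above 50%.

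**Conclusion.** The mismatch is real and minor. Followed as written, the AESI rule leaves out a confirmed, non-serious case of iron overload with persistently raised ferritin and TSAT not persistently above 45%, although 8.1.2 recognises such a case as iron overload. This assumes that the event is judged non-serious and is not reportable as an IND safety report; otherwise it would be collected.

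The effect cannot be quantified. The documents give no incidence of confirmed iron overload and no split by index, so any number of missed cases would be a guess. It would also go too far to say that each missed case alters a safety conclusion: the SAP sets no safety hypotheses and plans no inferential testing of adverse events. The primary endpoint, the sample size and power are unaffected.

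**What to change.** For counting and reporting only, extend the AESI definition in protocol 9.5.2 and SAP 3.6.1 to biopsy or MRI findings consistent with iron overload, together with persistent elevation of either index that 7.5.2 already treats as elevated (TSAT or ferritin). List for each case which index was raised, so that the TSAT-only count can still be read off.

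Separately, 8.1.2 and 9.5.2 must be reconciled where they differ: biopsy and MRI against biopsy or MRI, and TSAT or ferritin against TSAT. What confirmed iron overload means for study drug is the sponsor's clinical choice, and the change to the counting rule does not depend on it.

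The cost is a wording change in 9.5.2 and in one SAP bullet, plus the reconciliation with 8.1.2. No new test or visit is needed. The downside is that the AESI count may be slightly less favourable.
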